## E. Study Procedures

Subjects will be asked to refrain from consuming alcoholic beverages and drugs during study participation, which will be verified by a urine drug quick test and breathalyzer. If results indicate non-compliance with these study procedures, subjects will be discharged from the study. Subjects will be instructed to drink their typical amount of caffeinated beverages in the morning to minimize caffeine withdrawal, which could confound the study measures. For outline of protocol per session and estimated timings, see Table 1. Briefly, sessions will include:

In person Screening Session: This session will involve: a) obtaining informed consent; b) smoking history and assessment of nicotine dependence severity based on FTND; c) CO levels will be measured ; d) urine cotinine of 3 (out of 6) or higher on the semi-quantitative cotinine dipstick will be measured to ensure smoking status and a urine sample will be collected for quantitative cotinine assay; e) screening for co-morbid psychiatry conditions using the MINI; f) physical examination including ECG and vitals; g) urine analysis for drug screening and urine pregnancy test; h) ) blood draws for: 1.) laboratory examination including CBC, ALT, AST, alkaline phosphatase, glucose, BUN, creatinine and 2.) DNA; i) SILS to measure estimated IQ.

Ad libitum Smoking Session: Those found eligible will complete the *ad libitum* smoking baseline assessment, consisting of self-report measures of mood, withdrawal and smoking urges, cognitive tasks and vitals. Biochemical measures will include CO levels, breathalyzer, urine toxicology for drug screening, urine cotinine, blood draws for: 1.) nicotine and nicotine metabolite levels and 2.) gonadal hormone levels (progesterone, estradiol).

Medication Initiation (Medication Days 1-2) and Abstinence Phase (Medication Days 6-7) Sessions: Those subjects who were found eligible will be randomized to medication

## COMT Inhibition as a Novel Treatment for Nicotine Addiction in Women

(tolcapone) or placebo, in a double-blind fashion. Urn randomization will endeavor to balance medication and placebo groups for race, baseline smoking rate, and menstrual cycle phase. Although genotype will not be known for all subjects prior to randomization, in cases when it is known (e.g., genetics sample collected at baseline is processed prior to randomization) will be counterbalanced for genotype as much as possible.

Brief once-daily visits during the medication initiation (Medication Days 1-2) and abstinence periods (Medication Days 6-7) will serve four purposes: 1) administer pill in person and give take-home doses with instructions (100mg three times a day (TID); subjects will be asked to self-administer the take-home doses at approximately 6-hour intervals); 2) screen for adverse medication effects (Adverse Events Form; heart rate and blood pressure); 3) check for nicotine abstinence compliance (expired CO; urine cotinine; self-reported cigarettes per day); 4) collect self-report measures of withdrawal, smoking urges and mood, which are hypothesized to fluctuate with abstinence and/or medication.

Medication Initiation and Stabilization Phase (Medication Days 1-5): For the first five days of medication, subjects will be told they may smoke their cigarettes as much as they choose (*ad libitum*). They will be asked to attend one brief session per day on Medication Days 1-2. These first days will allow the participants to achieve medication optimal dosing and steady state levels prior to initiating the abstinence period. For Medication Days 3-5, the subjects will maintain the same dose and take the doses at home. During these days, they will have either in person/or phone check-in with a member of the research team to check for reported adverse effects. Brief questions about smoking (e.g., cigarettes per day) and whether they noticed changes in mood or smoking urges will also be asked. These phone check-in days are designed to maintain contact to continue monitoring for safety purposes, while reducing the burden on the participants. Subjects will have an emergency contact so they can access care if needed during this time.

Abstinence Medication Maintenance Sessions (Medication Days 6-7): Beginning on the evening of Medication Day 5, subjects will be asked to refrain from smoking their cigarettes. They will be asked to attend one brief check-in session per day on Medication Days 6-7. Medication doses continue at 100mg TID during this phase. Smoking abstinence will be tracked with CO-levels, urine cotinine screens and self-report.

Post-2 ½ day Abstinence End of Trial Session (Medication Day 8): At the testing session, participants will have been abstinent from smoking for 2 ½ days or more (e.g., 8PM Medication Day 5 through 8AM Medication Day 8), and maintained on tolcapone (or placebo) for the previous week. Participants will take their final dose (100mg) on the morning of Medication Day 8 then complete the same self-report measures and cognitive tasks from the baseline *Ad libitum* Smoking session. Blood will be collected for assessment of nicotine and cotinine (as additional confirmation of abstinence), gonadal hormones and liver function tests (to screen for adverse effects of tolcapone).

Subjects will then complete the Smoking Choice Laboratory Procedure. As we have done in previous studies, participants will complete this paradigm in a designated, negative pressure room. After sample smoking (2 sec cigarette puffs separated by a 20 sec interval) to measure subjective responses to smoking following abstinence, participants exchange tokens for cigarette puffs (2 puffs) or money (\$0.75) every 9 minutes until 1.5 hours had elapsed (i.e., 9 min x 10

## COMT Inhibition as a Novel Treatment for Nicotine Addiction in Women

tokens). This token value is sensitive to increases and decreases in smoking behavior (Sofuoglu *et al*, 2009). If participants choose cigarette puffs instead of money at every opportunity, they will smoke the equivalent of slightly more than one cigarette within the 90-minute laboratory paradigm. Participants will be allowed to decline the sample smoking opportunity if they wish to remain abstinent. Even if they decline the sample smoking opportunity, they will still be asked to remain at the lab for the remainder of the 90-minute paradigm. If they decline this smoking sample opportunity they will also still be allowed to exchange all un-traded tokens for take-home pay (totaling \$7.50 if they choose not to trade any tokens for “puffs” of the cigarette) at the end of the 90-minute paradigm.

At the end of this session, participants will stop medication at this time.

1-Week Follow-up Check-in Session: After medication is ended but prior to the in person check-in session, subjects will have the ability to check-in by as needed and will have an emergency contact so they can access care if needed. Approximately one week after the final medication day, participants will be asked to attend a brief in person follow-up check-in session. During this session, they will be asked about reported adverse effects, past week smoking and substance use and whether they noticed changes in mood or smoking urges. They will be asked to complete some questionnaires on these topics. Blood pressure and heart rate will be collected. A urine pregnancy and cotinine screen will be completed. CO levels will be collected. A blood sample will be collected for laboratory tests, including liver functions. Subjects will be discharged at the end of the follow-up session.

### ***Protection of Subjects***

In order to participate in a study, each subject must give informed consent. All potential risks will be described in detail to the subjects in the consent form. Confidentiality in this study is of the utmost importance to us. All information obtained will be stored in coded form. The names of the subjects will be used in hospital records.

Confidentiality will be protected by having records identified by code number only with the master list including names kept in a sealed envelope in a locked file in the Principal Investigator's office and by the pharmacy. Subjects will be given telephone numbers to call in case of emergency, 24 hours a day. The potential risk of loss of confidentiality due to data sharing will be minimized by creating de-identified data sets that exclude direct and indirect identifiers. In addition, researchers requesting data will be required to enter into a data sharing agreement. In addition, a Certificate of Confidentiality is being applied for to add some further protections against the research team being compelled to disclose information about participants.

This project will be monitored by the Center's Data and Safety Monitoring Board (DSMB) because the study involves the double-blind treatment of tolcapone and placebo. This board is composed of persons not otherwise affiliated with the clinical study who are experienced in various aspects of the conduct of clinical trials for the treatment of addictive disorders. We propose three investigators located here in Connecticut who are not directly involved in this study – [name]., [name]., and [name]. as the members of

the DSMB. The members of the DSMB, and all study Investigators, will complete Conflict of Interest forms created by VA HSS in accordance with NIH guidelines.

#### Individual Stopping Rules:

For the purposes of participant safety and data quality control, subjects will be discharged from the medication trial if: 1) subject experiences serious side effects which appear related to the study medication including liver toxicity (LFT>2 times greater than the upper limit of the normal range); 2) study physician/medical monitor decides that continued study participation may cause physical or psychological harm to the subject; 3) subject misses 3 consecutive medication-administration study sessions; 4) subject misses 2 consecutive CO level tests, urine cotinine tests during the abstinence phase; 5) subject is found to have used alcohol, illegal drugs or other psychotropic drugs during the medication phase of the study. In the case of any of these causes of early discharge from the trial, participants who began the medication phase of the study- even if they did not complete the medication phase- will still be contacted for phone follow-up and invited to attend the in person follow-up check-in for safety purposes.

#### Study Stopping Rules:

For the purposes of safety, if more than three subjects are stopped from medication use early due to serious side effects which appear related to the study medication, including but not limited to increased LFTs, twice as high as the upper limit of the normal range, which is not resolved by one-week follow-up, the co-PIs will confer with the DSMB to check whether the entire study should be halted.

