### B. Outcome Measures

COMT Inhibition as a Novel Treatment for Nicotine Addiction in Women

Table 1. Schedule of Assessments and Interventions	Time (min)	Screen	Ad Libitum Baseline	Brief Medication Visits Ivisit/day, 4 days	2 ½ day Abstinence End of Trial	1-week Follow-up
Screen & Baseline Measures & Smoking Behavior Measures						
Psychiatric and Medical Screen	35	X				
Demographics, Menstrual Cycle (MCAQ)	7		X			
Smoking History, Nicotine Dependence(FTND), urine cotinine dipstick	5	X				
Timeline Followback	5		X			X
Pill Administration, Abstinence Adherence and Physiological Measures						
Tolcapone or Placebo	2			X	X	
CO levels, Breathalyzer, urine cotinine	2	X	X	X	X	X
Urine toxicology	3	X	X	X (day 1)	X	
Urine pregnancy screen	3	X		X (day 1)	X	X
Vitals (HR, BP)	2	X	X	X	X	X
Blood Draws						
Genetics (rs4680)	3	X				
Labs for liver function	3	X			X	X
Nicotine, Cotinine, Hormones	3		X		X	
Self-report Measures of Withdrawal, Craving, Drug Effects, Mood and Impulsivity						
Withdrawal (MNWS); Smoking Urges(BQSU)	6		X	X	X	X
Subjective Nicotine Effect (DEQ)	2		X		X	
Adverse Drug Effects (AEF)	3			X	X	X
Depression (CES-D); Anxiety (STAI)	8		X		X	X
Affect (PANAS)	3		X	X	X	X
Impulsivity (BIS-II, BIS/BAS)	7		X			
Cognitive Tasks						
IQ	10	X				
Memory; Learning (digit span, HVLT)	25		X		X	
Sustained Attention (RVP, CPT)	10		X		X	
Cognitive Flexibility (CGT, SOC, Stroop))	10		X		X	
Laboratory Smoking Behavior						
Smoking Choice Paradigm	90				X	
TOTAL ESTIMATED TIME (hours):		1	1 ¾	1 ½ (20min/visit)	3	½

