### *Biochemical*

Genetics: Blood samples for DNA extraction will be collected at screening to examine whether the Val158Met single nucleotide polymorphism (SNP) of the COMT gene modifies the effects of nicotine. To protect confidentiality, each subject's blood sample will be encoded with a numeric designation and the name of the individual will be stored in a separate database. The samples will be transferred to the Genetic Laboratory at the VA medical Center for processing and storage.

Laboratory Bloods: Standard laboratory blood screening will include liver and thyroid function tests, CBC, serum electrolytes, BUN, creatinine, PT and PTT. This will be done at screening, again at the post-2 ½ day abstinence testing session and at the 1-week follow-up.

Urine screens: Urine pregnancy screens will be administered at screening, *ad libitum* baseline, prior to medication initiation, and prior to Smoking Choice Paradigm at the post-abstinence final session and at the 1-week follow-up. Urine drug screens will be administered at screening, *ad libitum* baseline, prior to medication initiation, and at the post-abstinence final session. Urine cotinine levels will be measured at baseline and check-in sessions and at post-abstinence testing session.

Serum estradiol and progesterone analysis: Serum estradiol and progesterone levels will be measured before the *ad libitum* smoking baseline and post-abstinence final session for use as covariates in our analysis, since female sex hormones may contribute to variation in women's response to nicotine or withdrawal (Allen *et al*, 2009b; DeVito *et al*, 2013) or women's smoking cessation ability (Allen *et al*, 2008a).

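### The rule for consulting the DSMB about halting the study cannot count a liver-test elevation first found by a scheduled test in a woman who completed dosing

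*Protocol*

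**What the plan says.** Protocol, Study Stopping Rules: the trigger operates "if more than three subjects are stopped from medication use early due to serious side effects" that look related to the medication. Raised LFTs, at twice the upper limit of normal, appear in the same sentence as a non-exhaustive example, followed by "which is not resolved by one-week follow-up, the co-PIs will confer with the DSMB". The stated outcome is a discussion of whether to halt the whole study.

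Protocol, Individual Stopping Rules: a woman is discharged from the medication trial for serious related side effects, including an LFT above twice the upper limit. Women discharged early are still contacted and "invited to attend the in person follow-up check-in for safety purposes".

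LFT schedule: Table 1 has a row "Labs for liver function" marked at screening, the end-of-trial session and the one-week follow-up. The Laboratory Bloods paragraph agrees: "This will be done at screening, again at the post-2 ½ day abstinence testing session and at the 1-week follow-up".

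Day 8 (Section E, Study Procedures): "Participants will take their final dose (100mg) on the morning of Medication Day 8 then complete the same self-report measures" and the cognitive tasks. The blood draw is described next, covering nicotine and cotinine, "gonadal hormones and liver function tests (to screen for adverse effects of tolcapone"). The session closes with: "At the end of this session, participants will stop medication at this time". The Overview likewise ends medication for everyone at that session.

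The SAP covers power and the efficacy analyses. It contains no safety rule.

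**The concern.** Liver toxicity is the only specific harm named in both stopping rules, and the protocol says the Day 8 LFTs are drawn to detect harm from tolcapone. One would expect those results to feed the only written study-level safety trigger. For women who complete dosing they do not, because the trigger counts premature stopping of medication and the scheduled tests fall when dosing is already ending or over.

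What is at stake is whether the DSMB must be consulted. Several women could show a related, persistent elevation without the protocol obliging anyone to raise it with the board.

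**Working it through.** The documents state no operating characteristic for this rule, so there is no figure to reproduce. The check sets the rule against the schedule.

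**Step 1. What the rule counts.** The subject of the sentence is women whose medication was stopped early. The LFT wording comes after a phrase introducing examples of the side effects that led to stopping. It is not a second, independent trigger. Early stopping is therefore a condition for every counted case, and the threshold is at least 4 women.

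**Step 2. When LFTs are scheduled** (Table 1; Laboratory Bloods; Section E). There are three time points: screening, Day 8 and the one-week follow-up. Two fall after dosing starts. None falls on Medication Days 1 to 7.

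**Step 3. When dosing ends** (Overview; Section E). Planned doses = 7 days × 3 + 1 on Day 8 = 22. Dose 22 is taken on the morning of Day 8 and is listed before the blood draw. Everyone stops by plan at that session.

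**Step 4. Combine.** A woman who has taken all 22 doses has her first LFT since screening when no dose remains to be withheld. The follow-up test comes about a week later. Neither result can make her someone who was stopped early.

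**Step 5. Possible patterns of an LFT above twice the upper limit, judged related, in a woman who completed dosing:**

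| Pattern | Counts as written? | Counts with the clause under fix? |
|---|---|---|
| (a) Raised on Day 8, not resolved at follow-up | No | Yes |
| (b) Raised on Day 8, resolved at follow-up | No | No |
| (c) First raised at follow-up | No | Optional, labelled as a single value |

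As written, 0 of 3 patterns count, whatever the true rate. Pattern (a) is the clearest omission: it meets the rule's own persistence requirement and fails only on early stopping.

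**Step 6. Where the rule does work.** A woman stopped during Days 1 to 7, for instance after an unscheduled test prompted by symptoms, does count. Because she is invited to the follow-up visit, where LFTs are drawn, the persistence wording can be applied to her.

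**Step 7. Whether other text closes the gap.** The individual rule acts by discharging a woman from medication, which has no effect once dosing is complete, and it adds no one to the study-level count. The Protection of Subjects section places the project under DSMB monitoring but sets no LFT threshold or trigger.

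**The case against.** The strongest reply is about intent. The only scheduled pair of LFTs after dosing starts is Day 8 and one week later, and the persistence wording fits that pair well. The authors may well have meant Day 8 elevations to count, which would make this loose drafting and not a decision to ignore them. That is plausible, but the sentence still requires early stopping, and a rule that decides when a safety board is consulted should not depend on inferred intent.

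A second reply is that little turns on it. The trigger leads to a consultation. Adverse events are recorded at every visit and phone check-in, the DSMB monitors the project generally, and nothing prevents the co-PIs from consulting it anyway. A woman who completed dosing is already off drug and is retested at one week. Exposure is 8 days, and women with a history of liver disease or with screening LFTs above twice the upper limit are excluded. All of this stands, and it limits the severity.

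Third, the protocol describes itself as a summary for local review alongside an application, and no DSMB charter is in the set. LFT results may be reported to the board by another route. The documents do not settle this either way; the finding concerns the rule as written.

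A reader might infer something stronger: that the persistence wording is inoperative for everyone, or that the early-stopping condition should be dropped for all serious side effects. Neither is supported. The wording works for women stopped early, and the gap shown concerns LFTs in women who completed dosing. Removing the condition altogether would widen the trigger beyond that.

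**Conclusion.** The point holds in this limited form. A related LFT elevation above twice the upper limit, first found by a scheduled test in a woman who completed dosing, contributes zero to the consultation count, including when it is raised on Day 8 and still raised at follow-up. This follows from the wording and the schedule and needs no assumption about event rates. It takes the order listed for Day 8 (dose, then blood draw) as the order of events.

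The consequence is bounded: a missed obligation to consult, with other monitoring in place and no efficacy result affected. A reader might infer that liver harm would go unseen, or that a trial that should stop would continue. The documents do not support that, because the tests are done and the board can be consulted at any time. A reader might also want a probability that the rule misses a signal. The documents give no elevation rate, so any such figure would reflect only the rate chosen.

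It is worth correcting because the rule omits results from the tests intended to detect the harm it names, and the correction is cheap.

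**What to change.** Keep the early-stopping trigger, the relatedness judgement and the more-than-three threshold. Add one alternative way of being counted: *or, having completed dosing, have LFTs more than twice the upper limit of normal on Day 8 that appear related to the study medication and remain unresolved at the one-week visit*.

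Elevations first found at follow-up may be counted too, but should be labelled as a single value whose resolution is not assessed, because women are discharged from the study at the end of that visit. Without that label, an unconfirmed follow-up value would be treated like a Day 8 elevation that had to persist for a week.

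The cost is a wording amendment to the Study Stopping Rules. It uses blood draws already planned and adds no visit. The downside is possibly more frequent DSMB consultation.

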#### **Payment:**

Subjects will be compensated for participation in each study visit up to a cumulative total of \$592.50, with longer visits compensated at a higher rate than brief visits (see details in Initial Review Application). Payments will be made in cash incrementally at each visit as follows: \$35 for the initial in-person screen; \$100 for the *ad libitum* smoking baseline session; \$40 for each of the four in-person check-in visits; for the weekday visit that is labelled an 'in-person' or phone check-in, subjects will be paid \$40 if they choose to attend the in-person check-in and they will be paid \$10 if they choose the phone check-in for that weekday visit (i.e., either medication day 3 or 5 depending on start date); for weekend phone check-in sessions subjects will always be paid \$10 for each of the phone check-ins; \$100 for the post-2 ½ day--abstinence session and \$50 for the smoking paradigm procedure and \$35 for the final one-week follow-up in-person check-in visit. Included in the total possible compensation will be the opportunity to earn an additional \$15 for study procedure compliance (e.g., \$15 for CO levels <8ppm with no increase in CO across abstinence visits), and the ability to take home money during the Smoking Choice Paradigm wherein smoking opportunities (i.e. 'puffs') are traded for tokens with monetary value. So if no tokens are traded for puffs, the subject can take home up to \$7.50 from the paradigm. The compensation schedule is designed to encourage study compliance while avoiding undue coercion to remain in the study. If the subjects choose to terminate a session prematurely, or a session is terminated early for medical reasons, they will receive full payment for that day. If

they become ineligible to continue in the study due to non-compliance with study procedures, they will only be paid for the portions of the study in which they have participated.

